2. PURPOSE

The purpose of this statistical analysis plan (SAP) is to ensure that the data listings, summary tables and figures which will be produced, and the statistical methodologies that will be used, are complete and appropriate to allow valid conclusions regarding the study objectives. Exploratory analyses not identified or defined in this SAP may also be performed to support the clinical development program.

2.1. RESPONSIBILITIES

INC Research will perform the statistical analyses and are responsible for the production and quality control (QC) of all tables, listings, and figures (TLFs).

2.2. TIMINGS OF ANALYSES

The primary analysis of safety and efficacy is planned after all subjects complete the final study visit or terminate early from the study and all relevant study data have been processed and integrated into the final locked data base.

3. STUDY OBJECTIVES

3.1. PRIMARY OBJECTIVE

The primary objective of this study is to assess the proportion of subjects who are pain-free at 2 hours postdose during the first double-blind (DB) treatment period (DB1).

3.2. SECONDARY OBJECTIVES

A secondary objective of the study is to assess the proportion of subjects who are pain-free at 2 hours postdose during the second double-blind treatment period (DB2).

Additional secondary objectives for each DB period are:

- To assess the proportion of subjects who are pain-free at 10, 15, 20, 30, 60, and 90 minutes postdose
- To assess the proportion of subjects who have pain relief at 10, 15, 20, 30, 60, 90, and 120 minutes postdose
- To assess the proportion of subjects with their most bothersome symptom (MBS) among nausea, photophobia, and phonophobia, absent at 10, 15, 20, 30, 60, 90, and 120 minutes postdose
- To assess the proportion of subjects who are free from nausea, photophobia, and phonophobia at each postdose time point
- To assess time to meaningful pain relief
- To assess time to pain freedom
- [REDACTED]
- To assess the proportion of subjects who have sustained pain freedom at 24 hours (2 to 24 hours) postdose (i.e., pain-free at 2 hours postdose, with no use of rescue medication or additional study medication and no recurrence of headache pain within 2 to 24 hours postdose)
- To assess change in functional disability score at 2 hours and 24 hours postdose
- To assess the proportion of subjects who use a second dose of the study medication or rescue medication after 2 hours (2 to 24 hours) postdose
- To assess treatment satisfaction at 2 hours postdose (7-point scale)
- To assess treatment satisfaction as measured by Patient Perception of Migraine Questionnaire-Revised (PPMQ-R) at 24 hours postdose
- Tolerability as assessed by adverse events (AEs) (also overall)
- Safety as assessed by clinical laboratory tests, vital signs, and electrocardiogram (ECG) (also overall)

3.3. EXPLORATORY OBJECTIVES

- [REDACTED]

Statistical Analysis Plan

Final V1.0

[name], Ltd.
Protocol #DFN-02-CD-012
INC Research #1007752

- 
- 
- 

3.4. BRIEF DESCRIPTION

[figure not shown]
This is a randomized, 2 DB treatment period dosing study, to be conducted at multiple centers in the United States. Previously diagnosed subjects with a history of episodic migraine (as defined by International Classification of Headache Disorders, 3rd edition [beta version]¹ [ICHD-3]), who experience an average of 2 to 8 migraine attacks per month for at least the past 12 months, with no more than 14 headache days per month, and with 48 hours of headache-free time between migraine headaches, will be randomized in a 1:1 ratio in both DB periods to receive either DFN-02 (sumatriptan nasal spray) 10 mg or a matching placebo. Subjects will treat 1 moderate to severe migraine attack in the DB1 treatment period and, if eligible, be re-randomized into the DB2 treatment period to treat another migraine attack at any pain level.

The duration of study participation will be up to approximately 13 weeks, including a screening period of approximately 3 weeks (wherein subjects may be randomized earlier than 3 weeks provided they meet inclusion/exclusion criteria and headache assessment criteria; the screening period may also be extended based on Investigator judgment and in consultation with the Medical Monitor), 2 DB treatment periods with up to 4 weeks (each period) for subjects to experience and treat migraine attacks, and 2 to 7 days for subjects to return to the site after treatment. The two DB treatment periods combined would total up to 10 weeks.

Subjects will record criteria in real-time in an electronic diary (eDiary) that will include, but is not limited to, the date and time of each migraine attack, the occurrence of aura, predose pain level, date and time of study medication use, postdose pain level, symptoms and functional disability, treatment satisfaction, and date and time of rescue medication. The eDiary will be reviewed for compliance and rescue medication.

The overall study design is presented in Figure 1.

Figure 1 Overall Study Design

3.5. SUBJECT SELECTION

Approximately 100 subjects will be randomized into the study. Subjects who do not qualify for enrollment after the screening period will be terminated as screen failures and will be replaced. Randomized subjects who discontinue study participation prior to study completion will not be replaced.

3.5.1. Inclusion Criteria

Subjects may be included in the study if they meet all of the following criteria:

1. Able and willing to provide written informed consent
2. Male or female, 18 to 75 years of age, inclusive, at screening
 - **Note:** If female and of childbearing potential (not surgically sterile or ≤ 1 year after the onset of amenorrhea due to menopause), the subject must (a) have a negative serum pregnancy test at screening and a negative urine test at Visit 2 (V2), (b) not be lactating, and (c) agree to practice a reliable form of contraception or abstinence during the study. Acceptable forms of contraception include implants, injectable contraceptives, combined oral contraceptives, an intrauterine device, a vasectomized partner, and double-barrier methods.
 - **Note:** If male (with female partner), the subject must agree to practice a reliable form of contraception or abstinence during the study.
3. A history of episodic migraine (as defined by ICHD-3), who experience an average of 2 to 8 migraine attacks per month for at least the past 12 months, with no more than 14 headache days per month, and with 48 hours of headache-free time between migraine headaches
4. Subjects who have migraine with or without aura. If migraine with aura, the aura cannot last longer than 60 minutes.

5. Subjects who, in the opinion of the Investigator, are willing and able to:
 - a. Evaluate and record pain, migraine symptoms, and study medication effectiveness information in real-time using an eDiary for the duration of the study;
 - b. Record each instance of the use of study medication and rescue medication in a subject eDiary in real-time for the duration of the study;
 - c. Comply with all other study procedures and scheduling requirements.
- 6. Subjects who can use the nasal spray device correctly after instruction

3.5.2. Exclusion Criteria

Subjects will be excluded from participating in the study if they meet any of the following criteria:

1. Minors, even if they are in the specified study age range
2. Medication overuse:
 - Opioids \geq 10 days during the 90 days prior to screening
 - Combination medications (e.g., Fiorinal[®]) \geq 10 days during the 90 days prior to screening (only applies if combination medication contains an opioid and/or barbiturate)
 - NSAIDs or other simple medications $>$ 14 days a month during the 90 days prior to screening
 - Triptans or ergots \geq 10 days a month during the 90 days prior to screening
3. Prior exposure to DFN-02 (or DFP-02)
4. Treated with onabotulinumtoxinA (Botox[®]) or other botulinum toxin treatment within 4 months prior to screening for migraine prophylaxis (subjects who were treated with same for cosmetic purposes may be allowed on a case-by-case basis after approval from the Medical Monitor)
5. On unstable dosages of migraine prophylactic medications within 30 days prior to and through screening
6. Taking mini-prophylaxis for menstrual migraine
7. Subjects with hemiplegic migraine, or other forms of neurologically complicated migraine
8. Subjects who have prolonged aura (i.e., more than 1 hour)
9. A history of stroke or transient ischemic attack
10. A history of migralepsy (seizure following a migraine) or a concurrent diagnosis of seizure disorder
11. Subjects who cannot differentiate between a migraine headache and tension-type or cluster headache
12. A history of more than occasional tension-type headache (based on Investigator judgment)
13. A history of cluster headaches
14. Known intolerance to sumatriptan (any formulation), or who have experienced a significant AE related to any triptan medication, including sumatriptan
15. Non-responsiveness to subcutaneous sumatriptan (\leq 6 mg dosage), in the opinion

- of the Investigator
16. Prior ischemic coronary artery disease (CAD): angina pectoris, history of myocardial infarction or documented silent ischemia or coronary artery vasospasm, including Prinzmetal's angina
 17. Wolff-Parkinson-White syndrome or arrhythmias associated with other cardiac accessory conduction pathway disorders
 18. Uncontrolled hypertension or systolic blood pressure (SBP) > 140 mmHg or diastolic blood pressure (DBP) > 90 mmHg (the values should be reconfirmed to rule out a transient fluctuation)
 19. Peripheral vascular disease or ischemic bowel disease
 20. Subjects using monoamine oxidase-A (MAO-A) inhibitor that cannot be completely washed out (at least 15 days)
 21. Selective serotonin reuptake inhibitors (SSRIs), serotonin norepinephrine reuptake inhibitors (SNRIs), tricyclic antidepressants, and steroids for chronic conditions, unless the dose is stable for at least 3 months prior to randomization and is not expected to change during the study
 22. Known intolerance to nasal sprays
 23. Subjects taking any medications or with illnesses likely to affect the physiology of the nasal mucosa (i.e., subjects with colds [upper respiratory infections], influenza, nasal septum surgery, or chronic nasal rhinitis)
 24. Any abnormal nasal physiology or pathology, or any other abnormal physiology and/or pathology that, in the opinion of the Investigator, would not allow the objectives of the study to be accomplished
 25. Acute sinusitis. Subjects may be rescreened 7 days after resolution of acute sinusitis infection/symptoms with no complaints of headache pain and if, in the opinion of the Investigator, it will not interfere with accomplishing the objectives of the study
 26. Chronic sinusitis
 27. Severe renal impairment (defined as creatinine > 1.5 × the upper limit of normal [ULN])
 28. Serum total bilirubin > 1.5 × ULN
 29. Serum aspartate aminotransferase (AST), alanine aminotransferase (ALT), or alkaline phosphatase > 2.5 × ULN
 30. Subjects with uncontrolled diabetes mellitus, or a glycosylated hemoglobin (HbA1c) > 7.9%, or with diabetes mellitus requiring insulin
 31. A history of alcohol or substance abuse (including marijuana) within 1 year that would compromise data collection
 32. A positive urine drug screen for recreational drugs, alcohol, marijuana (whether legal or not), or for prescription drugs not explained by stated concomitant medications:
 - a. Subjects consuming opioids for the treatment of migraine or using opioids or barbiturates temporarily for a legitimate medical cause may participate as long as they do not meet the medication overuse headaches (MOH) criteria.
 - b. Benzodiazepines are allowed if used for legitimate medical reasons.
 - c. Chronic use of amphetamines to treat attention deficit disorder (ADD) or attention deficit hyperactivity disorder (ADHD) and related disorders is

- allowed as long as the regimen has been stable for at least 3 months prior to screening and is expected to remain stable throughout the study.
- **Note:** For the above-mentioned conditions, the site must have appropriate documentation to justify the mentioned drug use (e.g., documented medical history and a valid prescription-based dispensation)
33. A history of or current neurological or psychiatric impairment, or cognitive dysfunction that, in the opinion of the Investigator, would compromise data collection
 34. Use of antipsychotics at least 15 days prior to randomization (if used for non-psychiatric conditions, should be evaluated on a case-by-case basis with the Medical Monitor)
 35. Subjects who received treatment with an investigational drug or device within 30 days prior to randomization, or within 3 months if associated with central nervous system
 36. Subjects who participated in a central nervous system clinical trial within 3 months prior to randomization
 37. Subjects who test positive for human immunodeficiency virus (HIV), hepatitis B surface antigen (HBsAg), or hepatitis C virus (HCV) antibody serology testing
 38. Subjects with any other medical condition that, in the judgment of the Investigator or Medical Monitor, would confound the objectives of the study (e.g., clinically significant abnormal thyroid-stimulating hormone [TSH] levels, cancer history** [except basal cell carcinoma], systemic lupus erythematosus).
**Exceptions to be made if the Investigator believes, with Sponsor approval, that the current status will not interfere with primary objectives
 39. Subjects who are employees or immediate relatives of the employees of the Sponsor, any of its affiliates or partners, or of the clinical study research site

3.5.3. Additional Exclusion Criteria

Subjects presenting with a history of hypertension that is uncontrolled during screening (i.e., SBP > 140 mmHg and/or DBP > 90 mmHg), whether on treatment or not, will be excluded. Subjects who had high or uncontrolled BPs in the past and are currently controlled with given therapies would be eligible for this study.

Independent of past history, if a subject has a sustained resting SBP > 140 mmHg and/or DBP > 90 mmHg at Visit 1 (V1) or V2, those subjects should be excluded. Any subject without a known history of hypertension that presents at screening with SBP > 140 mmHg and/or DBP > 90 mmHg should be excluded if the BP reading is due to suspected hypertension or another pathological condition, not if due to a transient fluctuation, based on the Investigator's evaluation. If the Investigator believes the BP is falsely elevated, they should repeat the assessment 2 to 3 times with the subject in a semi-reclined position in a quiet room. Subjects with persistent elevations, despite repeat assessments, should be excluded and referred to an appropriate healthcare provider for further assessment.

Statistical Analysis Plan

Final V1.0

[name], Ltd.
Protocol #DFN-02-CD-012
INC Research #1007752

3.6. DETERMINATION OF SAMPLE SIZE

Approximately 100 subjects will be randomized for the DB1 treatment period. Subjects who discontinue participation without completing the study protocol will not be replaced.

The primary endpoint is the comparison of the proportion of subjects who are pain-free at 2 hours after the first dose of study medication. It is assumed that 15% of placebo and 42% of DFN-02 10 mg (treated) subjects will be pain-free at 2 hours. A sample size of 50 subjects in each DB1 dosing arm will provide 86% power to detect this assumed difference between placebo and DFN-02 10 mg at a 5% (2-sided) level of significance.

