11.6 Methods of Analysis

11.6.1 Primary Efficacy Analysis

Efficacy analysis for primary, secondary, and exploratory endpoints will be based on the FAS population.

The primary efficacy endpoint, the proportion of patients who are free from headache pain at 2 hours after the first dose of study medication taken for a migraine attack with moderate to severe headache pain during the DB1 treatment period, will be analyzed using Fisher's exact test. The response rate will be calculated as the number of patients who are pain-free at 2 hours postdose divided by the number of patients with non-missing assessment at 2 hours postdose. The number of patients with non-missing assessment, the number of patients with response, the response rate, and the p-value for comparing DFN-02 10 mg versus placebo will be presented.

Analysis will be performed using the last observation carried forward (LOCF) and observed data in the FAS population and PP population.

Additional sensitivity analyses and data handling rules for missing data of the primary endpoint will be documented in detail in the SAP.

CONFIDENTIAL

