11.8 Determination of Sample Size

One hundred patients will be randomized for the DB1 treatment period. Patients who discontinue participation without completing the study protocol will not be replaced.

The primary endpoint is the comparison of the proportion of patients who are pain-free at 2 hours after the first dose of study medication. It is assumed that 15% of placebo and 42% of DFN-02 (treated) patients will be pain-free at 2 hours. A sample size of 50 patients in each DB1 dosing arm will provide 81% power to detect this assumed difference between placebo and DFN-02 at a 5% (2-sided) level of significance.

12 Quality Assurance and Quality Control

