5.4. FULL ANALYSIS SET

Each DB treatment period will have a Full Analysis Set (FAS). The FAS1 will include all randomized subjects who took at least one dose of study medication during the DB1 treatment period and have at least one post-baseline efficacy time point assessment in DB1. The FAS2 will include all re-randomized subjects who took at least one dose of study medication during the DB2 treatment period and have at least one post-baseline efficacy time point assessment in DB2. Subjects in the DB1 will be analyzed according to their randomized treatment. Subjects in the DB2 will be analyzed according to their re-randomized treatment. The FASs will be used for all analyses of efficacy endpoints.

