8. EFFICACY

8.1. PRIMARY EFFICACY ENDPOINT AND ANALYSIS

8.1.1. Primary Analysis of the Primary Endpoint

The primary efficacy endpoint is the proportion of subjects who are free from headache pain at 2 hours after the first dose of study medication taken for a migraine attack with moderate to severe headache pain during the DB1 treatment period (ie, headache pain rating of moderate [Grade 2] or severe [Grade 3] predose reduced to none [Grade 0] at 2 hours postdose). The primary efficacy endpoint will be analyzed using Fisher's exact test.

Proportions of subjects free from headache pain at 2 hours postdose will be calculated as the number of subjects who are pain-free at 2 hours postdose divided by the number of subjects with non-missing assessment at 2 hours postdose. Missing primary efficacy endpoint data will be imputed using the last observation carried forward (LOCF). Results based on the LOCF data and the observed data will be displayed separately.

The number of subjects with response, the number of subjects with non-missing assessment, proportions for the DFN-02 10 mg and placebo groups, 95% exact CIs for those proportions, the odds ratio for response, and the corresponding p-value will be presented for the comparison between two treatment groups for the FAS1. This analysis will exclude subjects who took a second dose of study medication or rescue medication prior to the data collection of the 2 hours postdose time point (inclusive). The analysis will also be performed using the PPS.

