15. INDEX OF TABLES

Number	Title	Population
14.1.1	Subject Disposition	Screened Set
14.1.3.1.1	Demographics and Baseline Characteristics	SS
14.1.3.1.2	Demographics and Baseline Characteristics	SS1
14.1.3.1.3	Demographics and Baseline Characteristics	SS2
14.1.3.2.1	Migraine History	SS
14.1.3.2.2	Migraine History	SS1
14.1.3.2.3	Migraine History	SS2
14.1.3.3.1	Migraine History - Migraine Symptoms	SS
14.1.3.3.2	Migraine History - Migraine Symptoms	SS1
14.1.3.3.3	Migraine History - Migraine Symptoms	SS2
14.1.3.4	Medical History	SS
14.1.4.1	Prior Medications	SS
14.1.4.2	Concomitant Medications	SS
14.1.4.3.1	Rescue Medications	SS
14.1.4.3.2	Rescue Medications	SS1
14.1.4.3.3	Rescue Medications	SS2
14.1.4.4.1	Study Medication Exposure	SS
14.1.4.4.2	Study Medication Exposure	FAS1
14.1.4.4.3	Study Medication Exposure	FAS2
14.1.4.5.1	Rescue Medication Exposure	SS
14.1.4.5.2	Rescue Medication Exposure	SS1

Statistical Analysis Plan

Final V1.0

[figure not shown]

[name], Ltd.
 Protocol #DFN-02-CD-012
 INC Research #1007752

Number	Title	Population
14.1.4.5.3	Rescue Medication Exposure	SS2
14.2.1.1.1	Primary Efficacy Analysis on Headache Pain Freedom at 2 Hours Postdose During DB1 Using LOCF	FAS1
14.2.1.1.2	Primary Efficacy Analysis on Headache Pain Freedom at 2 Hours Postdose During DB1	FAS1
14.2.1.2.1	Primary Efficacy Analysis on Headache Pain Freedom at 2 Hours Postdose During DB1 Using LOCF	PPS
14.2.1.2.2	Primary Efficacy Analysis on Headache Pain Freedom at 2 Hours Postdose During DB1	PPS
14.2.2.1.1	Secondary Efficacy Analysis on Headache Pain Freedom at 2 Hours Postdose During DB2 Using LOCF	FAS2
14.2.2.1.2	Secondary Efficacy Analysis on Headache Pain Freedom at 2 Hours Postdose During DB2	FAS2
14.2.2.2.1	Secondary Efficacy Analysis on Headache Pain Freedom at 10, 15, 20, 30, 60, and 90 Minutes Postdose During DB1 Using LOCF	FAS1
14.2.2.3.1	Secondary Efficacy Analysis on Headache Pain Freedom at 10, 15, 20, 30, 60, and 90 Minutes Postdose During DB2 Using LOCF	FAS2
14.2.2.4.1	Secondary Efficacy Analysis on Headache Pain Relief at 10, 15, 20, 30, 60, 90, and 120 Minutes Postdose During DB1 Using LOCF	FAS1
14.2.2.5.1	Secondary Efficacy Analysis on Headache Pain Relief at 10, 15, 20, 30, 60, 90, and 120 Minutes Postdose During DB2 Using LOCF	FAS2
14.2.2.6.1	Secondary Efficacy Analysis on Absence of Most Bothersome Symptom (MBS) among Nausea, Photophobia, and Phonophobia at 10, 15, 20, 30, 60, 90, and 120 Minutes Postdose During DB1	FAS1

Statistical Analysis Plan

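### SAP 3.6 claims 86% power where protocol 11.8 claims 81% on the same inputs; the planned Fisher's exact test gives 81.7%

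*SAP*

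**What the plan says.** The two sample-size sections share every input: 15% pain-free at 2 hours on placebo, 42% on DFN-02, 50 per arm in DB1, and a two-sided 5% level. They differ in the result.

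- Protocol 11.8: "A sample size of 50 patients in each DB1 dosing arm will provide 81% power to detect this assumed difference".
- SAP 3.6: "A sample size of 50 subjects in each DB1 dosing arm will provide 86% power to detect this assumed difference".

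Neither section names the test behind its figure. The analysis sections do, and they agree:

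- Protocol 11.6.1 says that the primary endpoint, for an attack "with moderate to severe headache pain during the DB1 treatment period, will be analyzed using" Fisher's exact test.
- SAP 8.1.1: "The primary efficacy endpoint will be analyzed using" Fisher's exact test.

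SAP section 11 lists changes from the protocol's planned analysis and does not mention power or sample size. Protocol 11.1 says the SAP prevails where the two differ, so the figure that formally stands is 86%.

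**The concern.** One design cannot have two powers for the same test. A reader who follows the precedence rule takes 86% and infers a 14% chance of missing the assumed effect. If the planned test delivers about 82%, that chance is about 18%, and the margin over the usual 80% is under 2 points instead of 6.

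The margin matters because both figures count all 50 per arm as analysed. No loss allowance is stated and discontinued subjects are not replaced. SAP 5.4 says "The FAS1 will include all randomized subjects who took at least one dose of study medication during the DB1 treatment period"; it also requires some efficacy reading after baseline. Randomized subjects who never dose therefore drop out. SAP 8.1.1 adds: "This analysis will exclude subjects who took a second dose of study medication or rescue medication prior to the data collection"; the cut-off meant is the 2-hour reading.

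**Working it through.** **Inputs** (protocol 11.8 and SAP 3.6): p₁ = 0.15 (placebo), p₂ = 0.42 (DFN-02), n = 50 per arm, two-sided α = 0.05. **Test** (protocol 11.6.1 and SAP 8.1.1): Fisher's exact.

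**Step 1. Reproduce the SAP's 86%.** Pooled normal approximation without continuity correction:

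power = Φ[(d − 1.96·SE₀)/SE₁]

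- d = 0.42 − 0.15 = 0.27
- p̄ = (0.15 + 0.42)/2 = 0.285
- SE₀ = √(2 × 0.285 × 0.715/50) = 0.0903
- SE₁ = √(0.15 × 0.85/50 + 0.42 × 0.58/50) = 0.0862
- (0.27 − 1.96 × 0.0903)/0.0862 = 1.08, and Φ(1.08) = 86.0%

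This matches the SAP. That the SAP used this formula is inferred from the match; it is not documented.

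**Step 2. Power of the planned test.** Sum over all outcomes (x of 50 on placebo, y of 50 on DFN-02):

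power = Σ Bin(x; 50, 0.15) × Bin(y; 50, 0.42), over tables whose two-sided Fisher p ≤ 0.05

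The result is 81.7%. The gap to the SAP is 86.0 − 81.7 = 4.3 points. The type II error is 100 − 81.7 = 18.3%, against the implied 14%.

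**Step 3. Compare methods at 50 per arm.**

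| Method | Power |
|---|---|
| Fisher's exact, enumerated | 81.7% |
| Continuity-corrected chi-square, enumerated | 81.7% |
| Walters corrected arcsine (approximates Fisher) | 80.9% |
| Continuity-corrected normal | 80.2% |
| Pooled normal, uncorrected | 86.0% |
| Arcsine, uncorrected | 86.7% |
| Uncorrected chi-square, enumerated | 86.8% |
| Unpooled normal | 88.0% |

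The Fisher-type and continuity-corrected methods give 80% to 82%, in line with the protocol. The uncorrected methods give 86% or more.

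**Step 4. Size needed for 86% with Fisher's test.** With equal arms, 55 per arm gives 85.4% and 56 gives 86.3%, so 56 are needed.

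**Step 5. Could an uneven split explain 86%?** Fisher power moves irregularly with the exact split. Over totals of 80 to 100 analysed, with arms differing by up to 12, the maximum is 84.9% (50 placebo, 49 DFN-02). With exactly 100 analysed the best is 84.2% (52/48).

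**Step 6. Sensitivity to losses.** The documents give no loss rate, so these sizes are assumptions.

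| Analysed (placebo/DFN-02) | Fisher power |
|---|---|
| 48/48 | 79.5% |
| 45/45 | 76.2% |
| 40/40 | 70.7% |
| 48/47 | 83.0% |
| 46/45 | 81.3% |
| 45/44 | 80.2% |
| 45/46 | 78.7% |

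Small equal losses take power below 80%, while some uneven splits stay above it. A missing 2-hour reading alone does not remove a subject from the main table: "Missing primary efficacy endpoint data will be imputed using the last observation carried forward (LOCF"), and the index of tables has a FAS1 table titled "Primary Efficacy Analysis on Headache Pain Freedom at 2 Hours Postdose During DB1 Using LOCF". This assumes that an earlier post-dose reading exists to carry forward and that the non-missing denominator in SAP 8.1.1 is counted after imputation. Such subjects are lost from the separate observed-data table.

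**The case against.** The strongest reply is that 86% is not an arithmetic slip. SAP 3.6 names no test, and a standard two-proportion formula returns 85.99% from its inputs. That is true, and the fault is better described as a figure for the wrong test than as a miscalculation. It does not rescue the sentence, which says what the design will provide for the primary comparison, and the only test planned for that comparison does not provide it.

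Second, the SAP says approximately 100 subjects and prints a whole percent. Slightly above 100, some splits round to 86%: 51/50 gives 85.8% and 50/53 gives 85.9%. This also stands, so the search in step 5 should not be read as a wide gap. But the SAP attaches its figure to 50 per arm, where the answer is 81.7%.

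Third, 81.7% rounds to 82%, not to the protocol's 81%. The protocol figure fits truncation or the Walters approximation (80.9%). That difference is under one point, but a corrected SAP should address it so that two numbers do not remain side by side.

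Fourth, attrition is a separate matter that affects the protocol's 81% equally. Agreed: it shows why the margin matters and is not evidence for the discrepancy.

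**Conclusion.** The concern holds. On identical inputs the documents state 81% and 86%, and the test both of them plan gives 81.7% at 50 per arm. The SAP figure is too high by 4.3 points and does not describe the planned analysis; the protocol's figure does, to within a point. The conclusion rests on the stated rates, 50 analysed per arm, and a two-sided Fisher test at 5%. It does not depend on how the 86% was obtained.

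The consequence is limited. Type I error, enrolment and the analysis do not change, and planned power remains above 80%. It should be fixed because the formally governing document overstates the power that justifies the trial's size.

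**What to change.** In SAP 3.6, replace 86% with the exact figure, 81.7% (82% if rounded). Name Fisher's exact test as its basis and state that it assumes 50 analysed per arm. Align protocol 11.8 with it, or add a short note that the protocol's 81% refers to the same test and differs only by rounding or approximation, if the sponsor confirms that. Record the correction in SAP section 11.

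Optionally, add power for a few smaller analysed sizes, labelled as assumptions.

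The cost is one sentence in SAP 3.6 and a line in section 11. The stated power becomes slightly less favourable; nothing operational changes.
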